5.5. Potential Benefits

There are no benefits to participating in this study. A potential benefit for the subjects randomized to the active (peanut) oral immunotherapy is the potential decrease in the subject's reactivity to peanuts after an accidental exposure/ ingestion of peanut. The likelihood of this is unknown.

6. Investigational Agent

6.1. Investigational Agent

6.1.1. Study Drug (Peanut Flour)

The investigational product in this trial is partially defatted peanut flour, 12% fat, light roast. This material is purchased from:

Byrd Mill Company [name]

Byrd Mill has stated that the peanut flour is manufactured under GMP for food products, no other nuts are processed at this peanut processing facility, and the peanut flour is not stored with material derived from other nuts. Analysis conducted to determine the peanut protein content in the bulk peanut flour has been done and a sample copy of the result is presented in the **Appendix 8**.

6.1.1.1. Formulation, Packaging, and Labeling

The raw material used in the manufacture of investigational product is peanut protein, manufactured by Byrd Mill Company. Raw material is accepted based upon review of the Certificate of Analysis, reproduced below.

The labels on Soufflé portion cups of investigational product and placebo are white, with dimensions 1 x 2.625 inches and the text is Arial font. The text that will appear on the labels is provided below:

Peanut Powder or Placebo

SUMC (Stanford University Medical Center)

[name], PhD, IND #: _____

Lot #: _____ Protocol #: 0001

Dose: _____

Keep refrigerated (2-8°C)

Caution: New Drug – Limited by Federal Law to Investigational Use

6.1.1.2. Dosage, Preparation, and Administration

The drug product consists of 27 different amounts of peanut protein, which are listed in **Table 1** and **Table 2** below. Each dosage of investigational product will be supplied in a 1oz (or other appropriately sized) Soufflé Portion Cup manufactured by Solo Cup Company (Highland Park, IL). The Soufflé Portions Cups are closed with plastic lids obtained from the same manufacturer. No other excipients are added to the peanut flour. The investigational product is supplied as a dry, tan powder, which should be stored in a cool, dry place at 2 - 8 °C.

Measuring, packaging and labeling will be done by:

Stanford University Medical Center

Clinical Food Research Unit (CFRU) cGMP

Stanford Packard El Camino Hospital, PEC, ^{1st} Floor

[name]

Mountain View, CA

Distinct peanut protein products will be measured and packaged using batch records for each dose. Each dose is filled at a ±5% tolerance by weight. Copies of completed batch records are available upon request. Each Soufflé portion cup containing the dose will be labeled and identified by a unique random assignment number and the dose number. A flow diagram describing the filling of Soufflé portion cups for each dose is presented below.

The CFRU cGMP unit complies with relevant sections of the Food Drug and Cosmetic Act (21 U.S.C. 351) for early phase products appropriate for a university-based clinical research program. Specifically, drug candidates are produced in compliance with current Good Manufacturing Practices (cGMP) as defined in 21 CFR 210 and 211. In addition, the cGMP unit adheres to pertinent sections of the July 2008 Guidance for Industry cGMP for Phase 1 Investigational Drugs. This document is intended to assist innovators involved with the manufacture of investigational drugs in early stage clinical trials. In order to manage the documentation requirements, Standard Operating Procedures (SOPs) and standards set forth in the aforementioned FDA Guidances and Regulations, the CFRU cGMP unit uses an electronic document control system and will be reviewed and supported from trained research and regulatory personnel.

A separate batch record is generated for each kit

6.1.2. Placebo (Oat Flour)

The placebo, oat flour, will be purchased commercially from the following manufacturer:

Arrowhead Mills, Inc.

A Division of the Hain Celestial Group. Inc.

Melville, NY 11747

Toasted oat flour, prepared as described in IND **sectors** is acceptable based upon being approved and used previously for IND **sectors**.

6.1.2.1. Formulation, Packaging, and Labeling

Packaging and labeling will be identical to that used for peanut flour as described under Section 6.1.1.1.

6.1.2.2. Dosage, Preparation, and Administration

Dosage, preparation, and administration will be identical to that used for peanut flour as described under Section 6.1.1.2.

6.2. Drug Accountability

Under Title 21 of the Code of Federal Regulations (21CFR §312.62) the investigator will maintain adequate records of the disposition of the investigational agent, including the date and quantity of the drug received, to whom the drug was dispensed (participant-by-participant accounting), and a detailed accounting of any drug accidentally or deliberately destroyed.

Original records for receipt, storage, use, and disposition will be maintained by the study site. An original drugdispensing log will be kept current for each participant. This log will contain the identification of each participant and the date and quantity of drug dispensed.

All records regarding the disposition of the investigational product will be available for inspection.

Following study drug/placebo administration, the site personnel will retain all empty or partially used vials. All drug material will be released and recorded by the nutrition personnel.

6.3. Assessment of Participant Compliance with Investigational Agent

Families will document daily dosing and any reaction from at-home dosing on diary logs. Monitoring of compliance will be performed by reviewing the participant's diary and monitoring and counting their returned study medication. Unused study medication will be brought back to the CFRU with each visit and collected by study staff for reconciliation of remaining peanut/oat flour.

6.4. Toxicity Prevention and Management

Reactions to Peanut OIT During Initial Dose Escalation Day

Participants may develop symptoms during the initial escalation. The investigator's judgment will be required to determine the best course of action with possible actions being:

1. Extend time interval between dosing (up to an additional 30 minutes).

- 2. Return to previously tolerated dose (i.e., repeat of last tolerated dose) then advance forward.
- 3. Discontinue protocol.

For oral or pharyngeal pruritus, the action should be to continue the normal dosing in 30 minutes.

For mild symptoms, defined as:

- skin limited or localized hives or swelling, skin flushing or pruritus
- respiratory rhinorrhea or sneezing, nasal congestion, occasional cough, throat discomfort
- GI mild abdominal discomfort or minor episode of vomiting

the action should be either to repeat the last dose in 30-60 minutes or to advance in 30-60 minutes depending on the physician's discretion.

For moderate symptoms, defined as:

- skin systemic hives or swelling
- respiratory throat tightness without hoarseness, persistent cough, wheezing without
- dyspnea
- GI persistent moderate abdominal pain/cramping/nausea, increased vomiting

the action should be to implement a 30-60 minute observation period and if symptoms resolve, reduce the dose by one step, repeat the same dose, or increase the dose by one step; if symptoms continue or worsen, the participant can be treated with antihistamines: if symptoms resolve, reduce the dose by one step, repeat the same dose, or increase the dose by one step; if symptoms require additional treatment, then consultation with the Principal Investigator is warranted to determine the next course of action.

For severe symptoms, defined as:

• respiratory — laryngeal edema, throat tightness with hoarseness, wheezing with dyspnea

- GI significant severe abdominal pain/cramping/repetitive vomiting
- neurological change in mental status
- circulatory hypotension

The initial escalation dose should be discontinued and the appropriate rescue medications administered.

If the subject requires treatment for symptoms with antihistamines on one occasion during the initial escalation protocol, then the rest of the protocol may be followed. If the subject requires more than one medication (e.g., albuterol, diphenhydramine, epinephrine, or others) or multiple doses of antihistamines, the initial escalation protocol should be terminated.

The PI will be available for questions and decision making for any questions related to the study protocol at all times.

All subjects will be observed for a minimum of 2 hours following administration of the final dose and will be discharged only when deemed clinically stable by a study physician.

Figure 3: Management of Symptoms During Initial Dose Escalation Day

Reactions to Peanut OIT During Build-up or Maintenance Phase

To be able to be eligible for an updosing or maintenance dose visit, subjects cannot have active wheezing, spirometry (as per manual of procedures) demonstrating FEV1 <80% predicted, or a current flare of atopic dermatitis that contraindicates updosing in the clinical judgment of the study physician. As needed, subjects will be maintained on their current dose of study product until their flare of asthma or atopic dermatitis is resolved.

If a subject has an updosing in the CFRU without symptoms, the action should be to continue per protocol with daily home dosing of the tolerated dose with the next updosing visit 2 weeks later.

If the subject only experiences oral/pharyngeal pruritus during the administration of the daily dose, then the same dose can be repeated the next day at home and continued throughout the interval unless other symptoms begin to develop.

For other mild symptoms (Objective, **APPENDIX 4**), the action should be either to repeat the dose the next day (day 2) at home or to have the subject return to the CFRU the next day (day 2) for a repeat of the previous day's dose or the last tolerated dose (at the study physician's discretion). If the dose is tolerated, then the subject will continue on that dose and return at the normal interval. If the dose causes mild symptoms again, then the subject may return to the CFRU the next day (day 3) and be given the last tolerated dose or a 1-2 step dose reduction. If tolerated, the subject will continue on this dose for the normal time interval. If mild symptoms recur, a 1-2 step reduction should be administered the next day (day 4). If tolerated then that dose should be continued for 2 weeks. If not tolerated, consultation with the PI is indicated.

If moderate symptoms (Grade 2, **APPENDIX 4**) occur, the action should be to have the subject return to the CFRU the next day (day 2) for dosing with the previous days dose or the last tolerated dose, at study physician discretion, under observation. If the dose is tolerated, the subject will continue on that daily home dose for the normal time interval per protocol. If the subject does not tolerate this dose, the subject should receive the last tolerated dose or a 1-2 step dose reduction the next day (day 3) in the CFRU or at home if the planned dose was previously tolerated. If this dose is tolerated, it will be continued as the daily home dose for the normal time interval, then escalation attempted in the CFRU as noted below. If this dose is not tolerated, then the next dose will be a 1-2-step reduction in dosing, and the dose will be given on the CFRU the next day (day 4). If this next dose is not tolerated, then a discussion with the PI will ensue to make a decision about whether to continue the subject on active treatment in the study.

If severe symptoms (Grade 3, **APPENDIX 4**) occur the action should be to treat the subject, and at the study physician's discretion either 1) have them return to the CFRU the next day (day 2) for dosing with a 2-step reduction in dose under observation or 2) discontinue them from the active treatment. If the subject tolerates the dose reduction, then they will remain on that dose for 2 weeks and then return to the CFRU for the dose escalation. A discussion with the PI may ensue to make a decision about whether to continue the subject on active treatment in the study.

If a subject fails dose escalation after three consecutive (with 2-4 weeks between) attempts, he/she will be considered a dose escalation failure and the last tolerated dose will be accepted as the maintenance dose.

For a completed dose escalation with no symptoms, subjects should be observed for 30 minutes. For mild symptoms, subjects should have a 1-2 hours post-protocol observation period. For moderate to severe symptoms, the observation period should be at least 4 hours and up to 24 hours based on symptoms and treatment regimen needed to stabilize the subject.

Any subject deemed to have severe allergic reactions to OIT, including hypoxia, hypotension or change in mental status and receives aggressive therapy (e.g., IV fluid resuscitation, mechanical ventilation, repeated doses of epinephrine for a life threatening reaction) at any time should be discussed with the PI and discontinued from active therapy.

For specific questions related to dosing escalation or continuation of the same dose that are not answered in the above protocol, the PI will be available for questions and decision-making.

Any subject who discontinues build-up dosing due to repeated allergic reactions to the characterized peanut allergen will have his/her blood drawn for mechanistic studies within approximately 1 week of discontinuation of therapy.

7.1. Concomitant Medications

7.1.1. Protocol-mandated

There are no protocol-mandated concomitant medications.

7.1.2. Other permitted concomitant medications

All subjects may continue their usual medications, including those taken for asthma, allergic rhinitis and atopic dermatitis, during the study. However, they must be able to discontinue antihistamines prior to the initial day of escalation, skin testing and all oral food challenges. Usual topical steroid use is permitted at the time of skin testing. Systemic (oral, IV, IM) steroid use longer than 5 days at one time or longer than 3 weeks (21 days) duration each year is not allowed. Up-dosing will not occur within 3 days of systemic steroid use.

7.2. Prophylactic Medications

There will be no prophylactic medications required in this protocol.

7.3. Prohibited Medications

- Omalizumab (Xolair)
- Systemic (oral, IV, IM) corticosteroids used for any greater than 5 days at one time or longer than a total of 3 weeks (21 days) duration each year for asthma. If used, subjects must not be up-dosed until at least 3 days after ceasing the administration of oral steroids
- Oral β-blockers

7.4. Rescue Medications

Treatment of individual allergic reactions during peanut OIT therapy should be with either an antihistamine and/or epinephrine, along with IV fluids, albuterol and steroids as indicated. Subjects and parents are likely to already have EpiPens[®], but for those who do not, a prescription for EpiPens[®] (or equivalent device) will be provided. Subjects and parents will be trained in proper use and will be able to demonstrate proper technique with the EpiPen[®] (or equivalent device).

Generally, for mild and moderate symptoms, the subject should receive antihistamines, and for more severe symptoms, the subjects should receive epinephrine, antihistamines, and then the other medications as indicated. If severe anaphylaxis occurs at any time, dose escalation will stop and the dose will be reduced to the last tolerated dose and the subject continued on that dose as long-term maintenance without further escalation.

Antihistamines

If a subject requires only antihistamines for treatment of allergic symptoms, the dose escalation can be continued. If symptoms during a build-up day require antihistamines in multiple doses or in combination with other medications (except epinephrine), there should be a dose reduction by 1-2 doses with the next dose given in CFRU. If dose escalation fails or requires treatment after two more escalation attempts each spaced 2 to 4 weeks apart, the dose should be reduced to the last tolerated dose and continued long term without further escalation.

Epinephrine

Any reaction (in CFRU or at home) that requires two or more doses of epinephrine will halt further dose escalation for this individual. Maintenance on the last tolerated dose would be continued.

CFRU

If a single administration of epinephrine is required during in CFRU escalation, the dose should be reduced by two doses, and the subject continued on that dose for four weeks. After 4 weeks at the reduced dose, an escalation attempt may be tried in CFRU.

If a single administration of epinephrine is required a second consecutive time during this escalation attempt, the dose should be reduced by two doses, and the subject continues on that dose for 6-8 weeks. After 6-8 weeks at the reduced dose, an escalation attempt may be tried in CFRU.

If a single administration of epinephrine is required a third consecutive time during this escalation attempt, the dose should be reduced by two doses and the subject continued on that dose as long-term maintenance without further escalation.

Home

If a single administration of epinephrine use occurs during dosing at home, this epinephrine use is not counted as one of the uses described above, unless severe anaphylaxis occurs at home. The subject should return to CFRU for an observed dose prior to resuming any dosing at home.

8. Study Procedures

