As stated above, an updosing attempt must be made within 3 clinic visits on a given dose, unless updosing is delayed due to administration of epinephrine as defined in Section 7.4 or illness. If the subject fails to successfully increase updosing for three consecutive attempts, updosing will be halted at the last tolerated dose and the subject will continue on that dose as their maintenance dose for the remainder of the study. The subject will be followed for the remainder of the study for safety and immunologic monitoring.

Vigorous exercise is not permitted for at least 2 hours after the dose of oral allergen immunotherapy. Also, there must be at least 1 hour between vigorous exercise and taking a dose of oral allergen immunotherapy. Allergic reactions are still possible when exercise takes place more than 2 hours after the dose.

Should significant systemic symptoms, which may include mild symptoms based on physician discretion or moderate or greater symptoms, be reported during the daily home dosing, the symptom/dosing algorithm will be followed to determine the best course of action. The appropriate treatment will depend on the type and number of symptoms. Subjects will be allowed to take their other daily medications during the build-up and maintenance phases of the study (i.e., antihistamines, albuterol) except where prohibited in this protocol.

Every 13 weeks during the build-up phase, subjects will have blood drawn for mechanistic labs, including basophil activation studies and pregnancy testing, if applicable. Blood will be collected prior to attempted dose escalations, but the decision to updose will be made based on clinical parameters, not the results of the assays.

Weeks 52, 65, 78, and 91– Maintenance Phase

Subjects will undergo updosing until reaching a daily maintenance dose of 4,000 mg and they will remain at that dose and return for follow-up visits at Weeks 52, 65, 78, and 91. Each of these visits will include a physical assessment, spirometry, skin test, and blood draw for mechanistic studies. Based on our previous data using a similar dosing method (Table 2), we expect all subjects on active treatment to reach 4,000 mg between the Week 44 and Week 78 visits.

Week 104 - On Study DBPCFC (to 4,000 mg)

At Week 104 all subjects will have a DBPCFC to 4,000 mg (as per staged challenge above) to assess desensitization. The visit will also include a physical assessment, spirometry, skin prick test and blood draw for mechanistic studies.

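### After a mild or moderate build-up-day reaction needing repeated or combined antihistamine treatment, Sections 6.4 and 7.4 give conflicting instructions on the next dose and, if mild, where it is taken

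*Protocol*

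**What the plan says.** **Section 6.4, reactions during build-up or maintenance.** The action depends on symptom grade.

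- Mild symptoms other than oral or pharyngeal itching: "the action should be either to repeat the dose the next day (day 2) at home", or a return to the CFRU the next day for the previous day's dose or the last tolerated dose, at the study physician's discretion.
- Moderate symptoms: the subject is seen in the CFRU on the following day, with this instruction: "for dosing with the previous days dose or the last tolerated dose, at study physician discretion, under observation".
- For mild symptoms, a step reduction is first named on day 3, as one of two options after a second mild reaction. The moderate pathway likewise first names it on day 3, if the day 2 dose is not tolerated.

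**Section 7.4, Antihistamines.** The action depends on the treatment needed. The trigger is: "If symptoms during a build-up day require antihistamines in multiple doses or in combination with other medications (except epinephrine". The action is: "there should be a dose reduction by 1-2 doses with the next dose given in CFRU". The same section says of treatment: "Generally, for mild and moderate symptoms, the subject should receive antihistamines".

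**Related text.** For the Initial Dose Escalation Day only, Section 6.4 adds a treatment-based rule to its grade-based ones: if a subject needs more than one medication "or multiple doses of antihistamines, the initial escalation protocol should be terminated". Section 8.3 refers to Section 7.4 when it sets the time limit for updosing attempts, but only for epinephrine: "unless updosing is delayed due to administration of epinephrine as defined in Section 7.4 or illness".

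**The concern.** The grade-based text in Section 6.4 makes no exception for how the reaction was treated. The treatment-based text in Section 7.4 makes no exception for grade. Because Section 7.4 names antihistamines as the general treatment for mild and moderate symptoms, one reaction can fall under both.

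What is at stake is the dose given the day after a reaction that needed repeated or combined treatment and, for a mild reaction, whether that dose is supervised. Two members of staff, each following the section in front of them, could act differently on the same case, and each could later be recorded as having deviated from the other section. Uneven handling would also add some variation to the pace of build-up.

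**Working it through.** The protocol gives no statistical figure on this point, so the check compares the texts and then uses Table 2 to size the difference.

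**Step 1. The overlapping case.** Take a mild or moderate reaction on a build-up day that needs two antihistamine doses, or an antihistamine plus another drug that is not epinephrine.

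| | Section 6.4 | Section 7.4 |
|---|---|---|
| Criterion | Symptom grade | Treatment needed |
| Next dose, mild | Same dose, or last tolerated dose | 1-2 doses lower |
| Setting, mild | Home permitted for the repeated dose; CFRU also an option | CFRU |
| Next dose, moderate | Same dose, or last tolerated dose | 1-2 doses lower |
| Setting, moderate | CFRU | CFRU |
| Strength of wording | should | should |

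For a moderate reaction the conflict concerns the dose only. For a mild reaction it concerns the dose and the setting.

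**Step 2. Where the texts agree.** If the reaction followed an updose, the last tolerated dose may be the dose one step below. If Section 7.4 counts its reduction from the dose that caused the reaction, giving that lower dose in the CFRU satisfies both sections. The conflict lies in Section 6.4's other option, the unreduced dose, which Section 7.4 does not offer.

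**Step 3. Is precedence stated anywhere?**

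- The multiple-antihistamine rule in Section 6.4 applies to the Initial Dose Escalation Day. The build-up text of 6.4 has no counterpart and does not refer to 7.4.
- Section 8.3 gives effect to 7.4 for epinephrine only.
- Section 6.4 makes the principal investigator available for dosing questions that the protocol leaves unanswered. This question is answered twice, differently.

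**Step 4. Size of the dose difference (Table 2).** Percentage reduction = 1 − (lower dose ÷ current dose).

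- Dose 20 (936 mg), one step: 1 − 749/936 = 20.0%. Two steps: 1 − 599/936 = 36.0%.
- Dose 12 (156 mg), one step: 1 − 125/156 = 19.9%. Two steps: 1 − 100/156 = 35.9%.
- Dose 26 (3,573 mg), one step: 1 − 2,858/3,573 = 20.0%. Two steps: 1 − 2,286/3,573 = 36.0%.
- Dose 27 (4,000 mg), one step: 1 − 3,573/4,000 = 10.7%. Two steps: 1 − 2,858/4,000 = 28.55%, about 29%.

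From dose 12 to dose 26 the difference is therefore about 20% to 36%. It is smaller at 4,000 mg.

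**Step 5. Possible effect on Week 104 eligibility.** The criterion of 13 weeks at maintenance implies reaching 4,000 mg by about Week 104 − 13 = 91. Sections 3.1 and 8.3 expect this between Weeks 44 and 78, which leaves 91 − 78 = 13 to 91 − 44 = 47 weeks of slack. The antihistamine text in 7.4 gives no duration for the reduced dose. If each lost step is assumed to cost one 2-week interval, one event costs 2 to 4 weeks, well inside that slack.

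**The case against.** The strongest reply is that the sections are layered. Section 6.4 gives a general set of options by grade, and Section 7.4 adds a narrower rule for reactions that needed heavier treatment. The protocol uses this pattern for the Initial Dose Escalation Day, and again where the epinephrine rules of 7.4 delay updosing. Section 6.4 also leaves room for the physician and includes an option that can meet both rules.

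Part of this stands. Layering is a reasonable guess at the intent, and the two sections are not incompatible in every case. But the protocol writes the layering down in those other two places and does not do so here. Section 6.4's discretion includes the unreduced dose; Section 7.4 leaves a choice only between one step and two.

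A reader might also infer three stronger points that the documents do not support.

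- **That Section 7.4 makes the reduction mandatory for any build-up reaction.** Both sections say should, and the 7.4 trigger is symptoms during a build-up day. Whether it reaches daily home doses between visits is unclear.
- **That the problem is common because Section 5.2 expects about 80% of subjects to have mild and 15% moderate symptoms.** Those figures cover any symptom at any time in dosing. The share needing repeated or combined antihistamine treatment is not given.
- **That Week 104 eligibility is materially affected.** Step 5 shows ample slack for a single event. Only repeated events in slow escalators could matter, and no figure supports that.

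**Conclusion.** The contradiction is real but narrow. It covers mild or moderate reactions on a build-up day that need several antihistamine doses, or an antihistamine with another non-epinephrine drug. In that case Section 6.4 permits an unreduced next dose, at home if the reaction was mild, while Section 7.4 says the dose should be reduced by 1-2 doses and given in the CFRU. No text sets precedence.

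Over the 25% steps of Table 2, the next dose under 7.4 is about 20% to 36% lower than a repeated dose. That comparison assumes staff take the repeat option in 6.4 and that steps are counted from the dose that provoked the reaction. Frequency is unknown. The effect on Week 104 eligibility is likely small, and the sample size and primary test are untouched. The point deserves correction because it concerns dose and supervision after a reaction that needed repeated or combined treatment.

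**What to change.** Reconcile the build-up text of Section 6.4 with the antihistamine text of Section 7.4:

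1. State in both sections one consistent rule for the next dose and its setting after a build-up reaction treated with more than one antihistamine dose or a non-epinephrine combination.
2. Say which section prevails when symptom grade and treatment given point to different actions, and add a cross-reference each way.
3. Say whether the rule covers reactions to home doses between visits.

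Which rule is right is a clinical decision for the sponsor and investigators; none is proposed here. The cost is wording in two sections of the protocol, with no change to the sample size or the analysis.

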Up-dosing phase (build-up phase) (Week 1-44): Subjects will receive subsequent doses (**Table 2**) at home for the next 14 days. Subjects who tolerate only 1.5 mg on the IDED will return in 7 days for updosing to 3 mg and then return 7 days later for updosing to 6 mg before proceeding to dose #6. Subjects who tolerate only 3 mg on the IDED will return in 7 days for updosing to 6 mg before proceeding to dose #6. Subjects will be instructed to continue dietary peanut avoidance throughout the entire study. They will also be instructed not to introduce any new foods to the diet and to continue avoidance of the subject's other known food allergens, if any. At 2-week intervals, the subjects will return for a possible increase in the daily oral dose until they reach 4,000 mg peanut protein build-up phase).

During dose escalation, there should be increased hydration (i.e. about 16 oz or more given orally) and restricted exercise for 2 hours after dosing.

Dose #	Dose	Interval (Weeks)	% of Increase
5	6 mg	2	Initial Dose Escalation Day
6	12 mg	2	100%
7	25 mg	2	108%
8	50 mg	2	100%
9	75 mg	2	50%
10	100 mg	2	33%
11	125 mg	2	25%
12	156 mg	2	25%
13	195 mg	2	25%
14	245 mg	2	25%
15	306 mg	2	25%
16	383 mg	2	25%
17	479 mg	2	25%
18	599 mg	2	25%
19	749 mg	2	25%
20	936 mg	2	25%
21	1,170 mg	2	25%
22	1,463 mg	2	25%
23	1,829 mg	2	25%
24	2,286 mg	2	25%
25	2,858 mg	2	25%
26	3,573 mg	2	25%
27	4,000 mg	2	12%

Table 2: Dail	y Peanut Protein	Dosing and Increas	se Schedule for	Build-Up Phase
---------------	------------------	---------------------------	-----------------	----------------

Subjects will begin the CFRU dosing schedule as outlined above until 4,000 mg of peanut protein is reached. Any updosing attempts may be postponed for 1-2 extra visits based on clinical judgment. However, an updosing attempt must be made within a maximum of 3 consecutive scheduled clinic visits. Subjects should withhold their daily home dose and any prophylactic antihistamines on the in-CFRU updosing day but should take all other prescribed medications. Note that the daily home dose should be taken as part of a meal at a consistent time (within 24±2 hours of the previous day's dose), and it is critical to take the dose every day. Doses should be separated by at least 12 hours. Subjects who require dosing reduction during the 2-week period due to illness will undergo an attempted updosing only after resuming their full dose for a minimum 3 days.

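### After a Grade 3 updosing reaction in the CFRU treated with one epinephrine dose, Section 6.4 sets a 2-week hold and Section 7.4 sets 4 weeks (6-8 after a second consecutive use), and 6.4 does not point to 7.4

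*Protocol*

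**What the plan says.** Protocol Section 6.4, under reactions during build-up or maintenance, gives the physician two options after Grade 3 symptoms once the subject has been treated. One is to discontinue active treatment. The other is to "have them return to the CFRU the next day (day 2) for dosing with a 2-step reduction in dose under observation". If the reduced dose is tolerated, "then they will remain on that dose for 2 weeks and then return to the CFRU for the dose escalation". A discussion with the principal investigator may follow, but is not required.

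Protocol Section 7.4 covers rescue treatment. It says that, as a general rule, "for more severe symptoms, the subjects should receive epinephrine, antihistamines, and then the other medications as indicated". For one epinephrine administration during CFRU escalation it then says "the dose should be reduced by two doses, and the subject continued on that dose for four weeks", after which another attempt may be made. After a second consecutive use there is again a two-dose reduction, and "the subject continues on that dose for 6-8 weeks". Two neighbouring rules in 7.4 narrow the case: severe anaphylaxis ends escalation, and so does any reaction needing two or more epinephrine doses.

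Protocol Section 8.3 contains the only link between the two. In the build-up phase an updosing attempt is due within three clinic visits on a given dose, "unless updosing is delayed due to administration of epinephrine as defined in Section 7.4 or illness". The same section also says that "updosing attempts may be postponed for 1-2 extra visits based on clinical judgment".

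**The concern.** Sections 6.4 and 7.4 can apply to the same reaction. Section 6.4 is triggered by its grade and Section 7.4 by its treatment, and 7.4 itself generally directs epinephrine for severe symptoms. The dose reduction agrees, but the time before the next attempt does not.

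The severe-symptom paragraph of 6.4 reads as complete: treat, reduce, hold, escalate. Nothing in it tells staff to look elsewhere if epinephrine was given. The error also runs in the less cautious direction. Staff who follow 6.4 literally would re-escalate a subject who has just needed epinephrine sooner than the rescue section allows. What is at stake is participant safety and uniform dosing, not a statistical quantity.

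**Working it through.** The plan gives no figure to reproduce. The check compares the two rules for one defined event and then sizes the group affected.

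**Event.** A Grade 3 reaction during CFRU updosing, treated with exactly one epinephrine dose, not severe anaphylaxis, with therapy continued.

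| | Section 6.4 | Section 7.4 |
|---|---|---|
| Dose reduction | 2 steps | two doses |
| Hold, first use | 2 weeks | 4 weeks |
| Hold, second consecutive use | 2 weeks (no separate rule) | 6-8 weeks |

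**Differences.**
- First use: 4 - 2 = 2 weeks. The 6.4 hold is 2/4 = 50% of the 7.4 hold.
- Second consecutive use: 6 - 2 = 4 to 8 - 2 = 6 weeks. The 6.4 hold is 2/8 = 25% to 2/6 = 33% of the 7.4 hold.
- Both events together: 2 + 2 = 4 weeks under 6.4, against 4 + 6 = 10 to 4 + 8 = 12 weeks under 7.4.

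**Does Section 8.3 remove the conflict?** Two provisions bear on it.
- The exception to the three-visit limit names 7.4 as the source of epinephrine delays. It lifts a maximum waiting time. It neither sets a minimum nor withdraws the 2 weeks in 6.4.
- Postponing by 1-2 of the two-weekly visits stretches the 6.4 hold to 2 + 1 x 2 = 4 weeks, or 2 + 2 x 2 = 6 weeks. That reaches the first 7.4 hold and the lower end of the second, but it is optional.

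**Does another clause in 6.4 settle it?** Its closing provision sends dosing questions to the principal investigator when the protocol leaves them unanswered. Here the protocol gives two different answers.

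**Size of the group.** Section 5.2 expects severe symptoms in under 1% of subjects at some point in dosing. Peanut OIT is assigned to 60 + 35 = 95 subjects (Section 13.1, Arms A and B). So 0.01 x 95 = 0.95, which is fewer than one participant on that expectation. The further conditions on the event shrink the group again, and a second consecutive use is rarer still.

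**The case against.** The strongest reply is that the protocol already shows which rule governs. Section 6.4 is a general rule by symptom grade, whereas 7.4 is triggered by one specific act in one setting. On ordinary reading the specific rule prevails, and 8.3 supports this by naming 7.4 as the source of post-epinephrine delays. The 2-week rule also has cases of its own: Appendix 4 counts blocked nostrils, a freely running nose and scratching to excoriation as Grade 3, and these need not be treated with epinephrine. Staff may always wait longer, may consult the principal investigator, or may stop treatment.

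Most of this stands. Section 7.4 is very likely the intended rule, and the event is rare. What does not follow is that 6.4 is harmless as written: permission to wait longer is not an instruction to do so, and the paragraph staff would turn to after a severe reaction still says 2 weeks without exception.

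A reader might also infer a second contradiction, over the long-term dose. Sections 6.4 and 8.3 keep the last tolerated dose after three failed attempts, while 7.4 keeps a two-dose reduction after a third consecutive epinephrine use. The documents do not establish an error here. Section 7.4 states its own version of the repeated-attempt rule for reactions treated without epinephrine, so that rule is probably not meant for the epinephrine track. The reduced dose ordered by 6.4 could also itself count as the last tolerated dose. No gap in final dose can be shown.

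**Conclusion.** The inconsistency is real but minor. For the event defined above, the hold before re-escalation is 2 weeks in 6.4 and 4 weeks in 7.4, or 2 against 6-8 weeks after a second consecutive use. Section 7.4 very likely governs, but 6.4 does not say so.

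The conclusion rests on the wording of Sections 6.4, 7.4 and 8.3. A manual of procedures is mentioned but is not at hand, and it may already settle the order of precedence. The count of fewer than 1 in 95 rests on the expectation in Section 5.2, which comes from earlier studies and is not a ceiling.

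A reader might infer that different hold periods could change who reaches maintenance in time for Week 104, and so disturb the primary comparison. The documents do not support that. On the protocol's own expectation the group is smaller than one participant, and the primary analysis and power do not depend on these hold periods.

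**What to change.** Add one sentence to the severe-symptom paragraph of Section 6.4 and nowhere else:

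> If a single dose of epinephrine was given during CFRU escalation and the subject continues therapy, the hold periods and consecutive-use rules of Section 7.4 (CFRU) apply instead of the 2-week hold; the discontinuation rules in Sections 6.4, 6.5 and 11.2 are unchanged.

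The limit to a single dose and the closing clause are both needed. A sentence covering any epinephrine use could be read as letting 7.4, which continues the last tolerated dose after two or more epinephrine doses, override the rules that stop therapy after life-threatening reactions or repeated epinephrine. The three-attempt sentences in 6.4 and 8.3 need no change.

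The cost is one sentence in the protocol and the matching line in any site dosing algorithm. It adds no visits, participants or analyses.
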